3.2.2 Exclusion criteria

- Age < 18 years old
- Bilateral subdural hematomas
- Subdural volume $< 115\text{cc}$
- Acute subdural hematoma
- Patient does not undergo surgical evacuation
- Other evidence of intracranial injury (i.e. epidural hematoma, intraparenchymal hemorrhage, skull fractures, subarachnoid hemorrhage, hydrocephalus)
- Patient's family not available for consent and requires emergent surgical evacuation
- Previous intracranial surgery
- Recent head trauma (< 1 week)

Title: Clinical Action of Curcumin/Turmeric In chronic Subdural hematoma recurrence (CACTIS)

- Use of anti-coagulation (i.e. Coumadin, Heparin, Apixaban, and Rivaroxaban) or anti-platelets (Plavix) drugs, with the exception of Aspirin
- Known coagulopathy disorders
- Positive urine or serum pregnancy test in pre-menopausal female subjects, without a documented history of surgical sterilization; or currently breastfeeding

1.1.1.□.1. Since the nuclear group in an older population, the pregnancy test will be made in exceptional cases.

- Allergy to curcumin or turmeric.
- Allergy to black pepper
- Markwalder Grading Scale

1.1.1.□.1. Score: 3-4

- Baseline dementia (for more than 6 months).
 - Adult who cognitively impaired for more than 6 months will be excluded from the study, since this impairment might be due to other reasons than cSDH, such as dementia or cognitive impairment.

4. Number of Subjects

This is a single center pilot study. A total of 48 subjects will be recruited in this study.

24 patients will receive placebo pills, and 24 will receive Curcumin (CC) pills. Patients will be first stratified according to their pre-surgery hematoma volume. Randomization will be performed within each hematoma volume group (12 subjects per hematoma volume group) to ensure equal distribution between placebo and CC groups.

Study Timelines

- Duration of an individual subject's participation in taking CC or placebo will be for up to a maximum of 60 days, with follow-up at 6 months and 18 months
- Clinical follow-up with CT scans will be up to 6 months, depending on if residual total hematoma volume < 80cc
- Enrollment of subjects will continue for 2 years.
- Complete data analysis will be performed within 2 years.

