cSDH patients will take one capsule three times a day for up to 60 days. Because maximum treatment duration is 60 days, IDS will dispense a total of 180 capsules. IDS will dispense this amount on two occasions to reduce waste and save cost for cases in which treatment may end early. They will undergo standard post-operative care in regard to imaging and clinical follow-up.

- Patients will begin taking placebo or CC within 24 hours post-operatively and able to take oral medication. It will then be continued TID.
- CT Imaging:
 - Pre-operative CT SOC scan
 - If the hematoma volume is < 115 cc, the patient will not be included in the study
 - Post-operative day one CT SOC scan within 24 hours of surgery.
 - Post subdural drain removal SOC scan usually 1-2 days after surgery.

Title: Clinical Action of Curcumin/Turmeric In chronic Subdural hematoma recurrence (CACTIS)

- If the residual total hematoma cavity volume is $<80\text{cc}$, the patient will be dropped from study, as the curcumin has not had time to influence the patient's reabsorption.
- *During the SOC one week follow-up appointment without a CT scan*, the attending will decide on the need for a repeat CT scan in 4 weeks based on the patient's **post-subdural drain removal SOC scan**.
 - If the residual total hematoma cavity volume is $\geq 80\text{cc}$, the patient will receive an additional CT scan (SOC) for an appointment one month following the previous appointment (Approximately post-operative day 37)
 - If there is a decline in neurological exam or other clinical concern, the neurosurgeon may perform an earlier CT scan
- This will continue on a monthly basis for 6 months, or until residual total hematoma cavity volume is $< 80\text{cc}$
 - **Resolution** will be defined as residual total hematoma cavity volume $< 80\text{cc}$
 - Patients with resolution of their hemorrhage will no longer require Tx or follow-up visits. Their pills will be returned and discarded. These patients will receive phone **call** follow-ups at 1-month, 6-month, and 18-month intervals

All radiographic imaging discussed here is our institution's standard of care for the management of SDH. If Tx discontinued, the patients will still be followed according to the schedule below

- Study Follow-Up **Phone Calls**
 - 1 month, 6 months, 18 months
 - Modified Ranking Scale (MRS) (Appendix 3)
 - Markwalder Grading Scale (Appendix 4)

5. Study Endpoints

5.1. Describe the primary and secondary study endpoints.

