 - c. For the next patient, we will first determine the hematoma cavity volume group; this patient's Tx assignment (CC or placebo) will be alternate to the immediately preceding patient. This process is repeated until all of the patients are enrolled.
3. The patients will start medication **within 24 hours after surgery**, or as soon as they are able to take oral medication
 - a. 1 capsule three times a day (with breakfast, lunch, and dinner) for a maximum of 60 days or until resolution of subdural hematoma
 - b. Resolution will be defined as residual total hematoma cavity volume $<$ 80cc
 - i. If the post-subdural drain removal scan demonstrates a residual total hematoma volume $<$ 80cc, the patient will not be included in the study sample; although, the patient may receive more than one dose of CC by the time of the CT scan.

- CT Imaging:
 - Pre-operative CT SOC scan-- If the hematoma volume is $<$ 115 cc, the patient will not be included in the study
 - Post-operative day one CT SOC scan
 - Post subdural drain removal SOC scan--If the residual total hematoma cavity volume is $<$ 80cc, the patient will be removed from study, as the curcumin has not had time to influence the patient's reabsorption.
 - During the SOC 1 week follow-up appointment, the attending will decide on the need for a repeat CT scan in 4 weeks based on the patient's **post-subdural drain removal SOC scan**. The considerations for re-evacuation include: lack of resolution of the initial clot, an obvious increase in size of the clot, persistent headache, onset of seizures, or onset of new deficit or headache. These criteria will be used in all subsequent considerations for surgical re-evacuation.

Title: Clinical Action of Curcumin/Turmeric In chronic Subdural hematoma recurrence (CACTIS)

- If the residual total hematoma volume is $\geq 80\text{cc}$, the patient will receive an additional CT scan (SOC) for an appointment one month following the previous appointment (Approximately post-operative day 37)
- If there is a decline in neurological exam or other clinical concern, the neurosurgeon may perform an earlier CT scan
- This will continue on a monthly basis for 6 months, or until residual total hematoma cavity volume is $< 80\text{cc}$
 - **Resolution** will be defined as residual total hematoma cavity volume $< 80\text{cc}$
 - Patients with resolution of their hemorrhage will no longer require follow-up visits. Their pills will be returned and discarded.

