This is a **pilot study** aiming to establish potential effect of CC on hematoma volume change as well as measurements and criteria for surgical intervention and cSDH recurrence. The sample size of 25 for each group is determined based on the patient population size and logistics of recruitment and will not reach the conventional statistical power of 80% or more unless the resolution rate of cSDH is 50% greater in CC than in placebo. To establish the effect size, we will compare CC and placebo groups by performing specific statistical analysis for each primary and secondary outcome: linear-mixed effects models for the trajectory hematoma volume over the period of up to six month (change and rate of change); survival analysis for time-to-resolution (since patients will be "censored" in their follow-up); Fisher's exact test and logistic regression for rate of surgical intervention or recurrence (criteria to be developed) as well as the rates of exiting symptoms removal and new symptom occurrence. These analyses serve multiple purposes: establish CC effects compared to the placebo; identify determinants of the various endpoints, and pilot-test working definition of recurrence etc. We will also report descriptive statistics and estimation, using confidence interval of 75% (instead of 95% used for large trials). The confidence interval will be interpreted with regards to the minimum clinically important difference (MCID). [name], PhD and Professor at the Division of Epidemiology, Biostatistics, and Preventive Medicine, Director of UNM CTSC Biostatistics, Epidemiology and Research Design Core, will serve as a co-investigator and oversee the statistical analysis and data interpretation. k

B. Laboratory Studies.

Experimental data on endothelial cell permeability after exposure to cSDH fluid at different concentrations of CC and the changes in protein expression will be quantified using Prism and GraphPad Prism software. Group comparisons using two-way analysis of variance (ANOVA) followed by Tukey's multiple comparison test will be performed to detect significance of differences between control (no treatment), IL-8-treated, IL-8/CC-treated, cSDH fluid-treated, and cSDH-fluid/CC-treated samples. For more detailed statistical analysis, we will use mixed model repeated measures with Wald tests between groups, followed by Sidak's family-wise error rate correction for multiple comparisons within each experimental group.

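### The time-to-resolution analysis has no term for post-drain cavity volume, although each patient's starting distance from the fixed 80 cc threshold partly determines the event time

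*Combined protocol and SAP*

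**What the plan says.** - **Method.** Under 9. Data Analysis, Statistical analysis, the whole specification for this endpoint is "survival analysis for time-to-resolution (since patients will be" censored). No test, model, stratification factor or covariate is named. The same paragraph also aims to "identify determinants of the various endpoints", but it names no determinant and does not link that aim to the treatment estimate. It plans 75% confidence intervals, to be read against a minimum clinically important difference.
- **Event.** In 9. Study Procedures, Interventions item 3, "Resolution will be defined as residual total hematoma cavity volume" below 80 cc. This is a fixed cut-off, not a change from the patient's own start.
- **Who is retained.** Under CT Imaging in section 4, if the post-drain scan shows less than 80 cc, "the patient will be dropped from study, as the curcumin has not had time to influence" reabsorption. No upper limit is set.
- **Allocation.** Section 4 says "Patients will be first stratified according to their pre-surgery hematoma volume" and "Randomization will be performed within each hematoma volume group". Study Procedures puts the cut at 140 ml.
- **Standing of the post-drain volume.** Background, CT Scans, cites it as one of three predictors of recurrence, alongside pre-operative volume and density. Endpoint 5.1.1 uses the post-drain scan as its reference, and Table 1 records total residual cavity volume at that scan.

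**The concern.** With a fixed threshold, the post-drain volume is the distance each patient has to travel. Two patients whose cavities shrink at the same rate will resolve at different times if they start at different volumes. Referring the change endpoints to the post-drain scan deals with this for change and rate of change. It does not do so for the time to reach a fixed line.

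Stratifying on pre-surgery volume balances post-drain volume only as far as the two are correlated. With about 24 patients per arm, some imbalance in starting volume is expected by chance, and the arm that starts lower will appear to resolve faster. The pilot exists to establish an effect size and to read a 75% interval against the MCID. If the one trial that is run shows a visible imbalance, that reading is less secure than the nominal level suggests. Leaving the model open also invites a choice of covariates after the imbalance has been seen.

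**Working it through.** **The plan's own figures.** The plan gives no figure for this analysis. Its only power statement (80% not reached unless resolution is 50% greater on curcumin) gives no placebo rate, alpha or test, so it cannot be reproduced. This point does not depend on it. Section 4 gives 24 per arm and the Statistical analysis gives 25; 24 is used here.

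**Step 1: threshold geometry.** The fall needed from a start V is (V - 80)/V.
- V = 82 cc: 2/82 = 2.4%.
- V = 160 cc: 80/160 = 50%.

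With exponential shrinkage and one assumed half-life of 110 days, the crossing day is 110 × log2(V/80):
- 100 cc: 110 × 0.322 = day 35.
- 130 cc: 110 × 0.700 = day 77.
- 160 cc: 110 × 1 = day 110.

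**Step 2: how much stratification helps.** For post-drain volume uniform on 80-130 cc, the SD of the difference in arm means under simple randomization is about (50/√12) × √(2/24) = 4.2 cc. For 80-160 cc it is about 6.7 cc. Simulated SDs with arms balanced within two pre-surgery halves:

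| Pre/post correlation (assumed) | 80-130 cc (simple: 4.19) | 80-160 cc (simple: 6.70) | Reduction |
|---|---|---|---|
| 0.3 | 4.08 | 6.52 | 3% |
| 0.5 | 3.82 | 6.11 | 9% |
| 0.8 | 3.10 | 4.97 | 26% |

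**Step 3: simulated trials.** From the protocol: 24 per arm, the 80 cc threshold, and monthly scans (days 37 and 67 are stated; 97, 127, 157 and 187 continue the monthly pattern). Assumed, because the documents give no volume distribution or shrinkage rate:
- post-drain volume uniform on 80-130 or 80-160 cc;
- median half-life 110 days (60 on drug), log-normal SD 0.5, 0.8 or 1.0;
- scan error SD 5 cc at follow-up and 0 or 5 cc at baseline;
- pre/post correlation 0.5, with arms balanced within the pre-surgery halves.

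There were three settings: A, effect throughout; B, effect ends at day 60; C, as B with 20% censored at random times. That makes 2 × 3 × 2 × 3 = 36 cells, each with 1,500 trials under effect and 1,500 under none. Cox models with Efron ties were fitted with treatment alone and with treatment plus linear post-drain volume.

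With no drug effect, a one-SE imbalance (3.7-6.4 cc) gave an unadjusted hazard ratio of 1.12-1.19 and an adjusted one of 0.98-1.01. The 75% interval spans about ×/÷ 1.40-1.46, so the shift lies inside it.

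Coverage of the 75% interval:

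| Trials | Unadjusted | Adjusted |
|---|---|---|
| All | 74-79% | 70-78% |
| Imbalance above 1 SE (about 32% of trials) | mean 68% (62-74%) | mean 74% (65-78%) |
| Imbalance above 1.5 SE | mean 62% (50-71%) | mean 74% (64-79%) |

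Power at the 5% level:

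| Setting | Unadjusted | Adjusted |
|---|---|---|
| A | 0.27-0.71 | 0.29-0.82 |
| B | 0.17-0.55 | 0.19-0.66 |
| C | 0.18-0.53 | 0.19-0.64 |

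The mean gain is 5 points (0 to 18). After equalising type I error it is 3 points, with 35 of 36 cells between -4 and +8. Type I error was 0.030-0.054 unadjusted and 0.035-0.069 adjusted. The SD of the log hazard ratio was 0.28-0.32 unadjusted and 0.30-0.35 adjusted. Monte Carlo SE is about 0.013 for power and about 0.02 per cell for coverage above one SE.

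**Step 4: other assumptions.** A separate simulation used starts of 80-100 and 80-120 cc, a drug shrinkage rate 1.5 times placebo, and log(volume/80) as the covariate. Imbalance correlated -0.44 to -0.76 with the unadjusted log hazard ratio. Power rose from 0.60 to 0.93 when patients' rates varied little (log SD 0.3) but only from 0.19 to 0.22 when they varied a lot (log SD 1.0). Null rejection was 3-6% unadjusted and 5-8% adjusted. A third run, with inputs close to Step 3 and 400 trials per cell, gave:
- correlations of -0.42 to -0.60 unadjusted and about 0 adjusted;
- null coverage above one SE of 66-74% unadjusted against 69-79% adjusted;
- power changes of -2 to +13 points.

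**The case against.** The strongest reply is that the unadjusted analysis is already valid. Averaged over all trials its 75% interval keeps its nominal coverage (74-79%), while the adjusted one drops to 70% in the worst cell, has a larger SD and reaches a type I error of 0.069. Concern about imbalanced trials is a preference for conditional coverage, and the cell ranges overlap. The plan never commits to an unadjusted analysis, since survival analysis can include Cox regression and determinants are to be explored. Every volume and shrinkage input is assumed. The cited evidence concerns recurrence, not time to resolution. The trial is a pilot that disclaims conventional power.

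Much of this stands. There is no average bias, the interval does not get narrower, power is a secondary argument, and the size is uncertain. The two SDs are not on one scale, however, because the adjusted hazard ratio is conditional on starting volume. The remaining points do not remove the gap. The link to event time follows from the threshold itself, and an unnamed determinant is not a prespecified adjustment. A reader of one imbalanced result needs an interval that holds for that result.

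The simulations also favour the plan in one respect: they assume sound randomization with balance kept among retained patients. Study Procedures describes alternating assignment and removes patients after it.

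One difficulty remains. Section 4 says "Patients will begin taking placebo or CC within 24 hours post-operatively", while the post-drain scan is usually 1-2 days after surgery, so the covariate may be measured after a first dose. The protocol's own position is that curcumin has not had time to act by then.

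**Conclusion.** The concern holds. The plan omits an adjustment for the variable that sets each patient's distance to the event, and nothing elsewhere in the document supplies it. This is a worthwhile, cheap improvement and not an error that invalidates the comparison.

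The benefit is mainly protection in trials with visible imbalance: average 75% coverage of 74% instead of 68% above one SE, and 74% instead of 62% above 1.5 SE. The power gain averages 3 to 5 points in the 36-cell simulation. The direction follows from the design. The size rests on assumed starting volumes, shrinkage rates, between-patient variability and pre/post correlation, so confidence in it is medium.

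**What to change.** State that the main time-to-resolution analysis is a Cox or discrete-time model with treatment and continuous post-drain total cavity volume, and give the unadjusted result as supportive. Fix the form of the covariate in advance (for example volume, or the log of volume over 80 cc). Use the same volume as baseline or covariate in the mixed model. The 140 ml group may be added to reflect the allocation scheme, but no power gain is claimed for it.

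The cost is analysis wording only, with no new scan, visit or patient. Four consequences should be acknowledged:
1. The hazard ratio becomes conditional on starting volume.
2. The interval will not be narrower.
3. With 24 per arm, type I error and coverage of the adjusted model should be checked before it is adopted.
4. The plan should state why the post-drain scan can serve as a baseline when a first dose may precede it.
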